randomized phase II trial of letrozole with or without palbociclib as first line treatment (PALOMA-1/TRIO-18) was conducted in postmenopausal women with HR+/ human epidermal growth factor receptor 2 negative (HER2-) metastatic breast cancer (12). At the time of the final analysis for progression-free survival (PFS) (median follow-up 29.6 months [95% CI 27.9–36.0] for the palbociclib plus letrozole group and 27.9 months [25.5–31.1] for the letrozole group), 41 PFS events had occurred in the palbociclib plus letrozole group and 59 in the letrozole group. Median PFS was 10·2 months (95% CI 5·7–12·6) for the letrozole group and 20·2 months (13·8–27·5) for the palbociclib plus letrozole group (HR 0·488, 95% CI 0.319–0.748; one-sided p=0.0004). The results of this trial led to FDA approval of palbociclib in combination with letrozole as first line therapy for patients with metastatic breast cancer. The recommended starting dose is 125 mg orally daily for 21 days followed by 7 days off in 28 days cycles in combination with letrozole 2.5 mg orally daily continuously. Most common adverse events from the phase II PALOMA-1 trial were neutropenia (48% grade 3), leukopenia (19% grade 3) and fatigue (36% grade 2) (12). Notably, despite the increased incidence of neutropenia, no neutropenic fever was reported. Dose delay was required in 45 % of patients in the combination arm and dose reduction was required in 40% of patients. Findings from the confirmatory trial PALOMA-2, a randomized phase III trial of palbociclib plus letrozole versus placebo plus letrozole for the first-line treatment of post-manopausal patients with ER+/HER2- advanced breast cancer is expected to be reported later this year. In second line setting, palbociclib plus fulvestrant demonstrated an improvement in PFS compared with placebo plus fulvestrant in the PALOMA-3 phase III trial (13). The median PFS was 9.2 months for the palbociclib-containing regimen and 3.8 months for the fulvestrant plus placebo arm.

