## **Permitted Concomitant Medications and Procedures**

All treatments the investigator considers necessary for a subject's welfare may be administered at the discretion of the investigator in keeping with the community standards of medical care. All concomitant medications will be recorded on the electronic case report form (eCRF).

Palliative radiation is permitted but palbociclib must be withheld throughout the course of radiotherapy. Palliative RT should not be delivered to a target lesion and it should not encompass more than 25% of the irradiated bone marrow. The reason for radiotherapy must be clearly documented and progression as per RECIST 1.1 must be ruled out. No dose modification of study treatment is mandated after completion palliative radiotherapy.

If elective surgery is needed during study, it is recommended the surgery be scheduled between treatment cycles. Palbociclib should be withheld 14 days prior to surgery. The next cycle of treatment may be delayed up to 4 weeks to allow for additional recovery at the discretion of the investigator.

All concomitant medications received within 28 days before the first dose of trial treatment and 30 days after the last dose of study drug should be recorded. Concomitant medications administered beyond 30 days after the last dose of trial treatment should be recorded for SAEs as defined in Section 11.

Antiemetic agents may be administered at the discretion of the investigator but are not commonly required as a prophylactic agent. All other manifestations of the subject's malignancy should be treated at the discretion of the investigator.

All other medical conditions should be treated at the discretion of the investigator in accordance with local community standards of medical care.

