#### **6.1.** Dose Modifications

#### 6.1.1. Palbociclib Dose Modifications

**Table 1. Dose Modifications for Adverse Reactions** 

Dose Level	Dose		
Recommended starting dose	125 mg/day		
First dose reduction	100 mg/day		
Second dose reduction 75 mg/day *			
*If further dose reduction below 75 mg/day is required, the subject will be			

\*If further dose reduction below 75 mg/day is required, the subject will be discontinued from study treatment.

Palbociclib will be withheld for drug-related >Grade 3 hematologic toxicities, non-hematological toxicity >Grade 3 including laboratory abnormalities and severe or life-threatening AEs as per Table 2 below.

Table 2: Dose modification guidelines for drug-related adverse events.

Toxicity	Grade	Hold Treatment (Y/N)	Timing for restarting treatment	Dose/Schedule for restarting treatment	Discontinue Subject
Hematological	1, 2	No	N/A	N/A	N/A
Toxicity	3* *Except lymphopenia (unless associated with clinical events, e.g, opportunistic infections)	Withhold initiation of next cycle.  Repeated hematologic monitoring one week later	Toxicity resolves to Grade ≤2	No dose adjustment is required	Toxicity does not resolve within 4 weeks of last study drug administration Permanent discontinuation should be considered for any
	Grade 3 ANC (<1000 to 500/mm³) + Fever>38.5° C and/or infection  Grade 3 Plt count (<50000 to 25000/mm³) with clinically	Yes	Toxicity resolves to Grade \leq 2 (ANC > 1000/ mm  , platelets > 50000/mm  )	Resume at next lower dose	severe or life- threatening event
	significant bleeding  4*  *Except lymphopenia (unless associated with clinical events, e.g, opportunistic infections)	Yes	Toxicity resolves to Grade ≤2	Resume at next lower dose	
Non-	1,2	No	N/A	N/A	N/A
hematological toxicity†  Note: Exception to be treated similar to grade 1 toxicity  Grade 2 alopecia Grade 2 fatigue	3,4 (if persisting despite medical treatment)	Yes	Toxicity resolves to:  • Grade ≤1; • Grade ≤2 (if not considered a safety risk for the subject)	Resume at next lower dose	Toxicity does not resolve within 4 weeks of last study drug administration Permanent discontinuation should be considered for any severe or life-threatening event

Footnotes:  $\dagger$ Concurrent elevation of bilirubin > 2x ULN and ALT > 3 x ULN in absence of an evident alternative explanation (such as liver mets) will lead to discontinuation of the study drugs

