#### Footnotes:

- 1: For cycle 1 only: labs do not need to be repeated if done within 7 days of day 1.
- 2: Blood Chemistries to include: sodium, potassium, serum creatinine (or GFR; see 3.1.8), calcium, albumin, ALT, AST, bilirubin, alkaline phosphatase.
- 3: For Cycles 1 and 2 only, hematology assessments done on Day 1 and also on Day 15
- 4: A negative serum or urine pregnancy test is required within 72 hours of study registration and at the beginning of each cycle, if clinically indicated. If the urine test cannot be confirmed as negative, a serum pregnancy test will be required.
- 5: For subjects with unresolved treatment-related toxicity, follow as medically appropriate until resolution or stabilization
- 6: Survival assessment to be recorded every 3 months until 2 years from registration
- 7: Appropriate scans to assess disease status will be obtained within 28 days of study enrollment including CT chest, abdomen/pelvis. PET/CT: The CT portion of PET/CT is usually of lower quality and should typically not be used in place of dedicated diagnostic CT. However, if the CT portion is of diagnostic quality, it may be used.
- 8: Disease assessment will be performed on Day 1 of every 2 cycles starting at cycle 3 (ex. Day 1 of cycle 3, 5, 7, etc.) for the first 19 cycles (18 months). Disease assessment will be performed on Day 1 of every three cycles starting at cycle 22 (ex. Day 1 of cycle 22, 25, etc.) until discontinuation of study drug.
- 9: Bone scan will be repeated as per footnote 8 above only if positive for bone mets at the time of screening or if clinically indicated.
- 10: If bone lesion(s) detected from whole body bone scan, perform bone x-ray, CT or MRI of the largest bone metastatic area.
- 11: Histological confirmation of breast cancer diagnosis is required (Section 3.1.3). Although not required as a protocol procedure, a patient with a new metastatic lesion should be considered for biopsy whenever possible to reassess ER/PR/HER2 status, if clinically indicated. Also, biopsy at the time of progression should be considered as clinically indicated, but it is not required as a protocol procedure. If a biopsy is prospectively done as standard of care, the study would like to collect samples for correlative research. Unstained slides from either the fresh biopsy or from an archival tumor specimen (metastatic lesion) may be submitted at baseline.

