## 7.3. Every two cycles ( $\pm 7$ days)

- Disease assessment will be performed every 2 cycles starting at cycle 3 (cycle 3, 5, 7, etc.) for the first 19 cycles (18 months):
  - o CT/MRI chest, abdomen, pelvis (±7 days).
  - o Whole body bone scan if positive for mets at screening or if clinically indicated.

- o If bone lesion detected from whole body bone scan, repeat bone scan, bone X-ray, CT, or MRI of the largest skeletal lesion identified.
- o If skin lesion detected by physical exam at screening, skin color photography.
- Subjects will be assessed every 2 cycles starting after cycle 5 (cycle 7, 9, 11, etc.):
  - o Physical exam, weight
  - o Vital signs
  - o ECOG performance status
  - o Blood chemistries (sodium, potassium, serum creatinine calcium, albumin, ALT, AST, bilirubin, alkaline phosphatase)
  - o Platelets, ANC and hemoglobin
  - Pregnancy test for women of childbearing potential (WOCP), if clinically indicated. If the urine test is positive or cannot be confirmed as negative, a serum pregnancy test will be required.
  - o Assess adverse events
  - Concomitant medications
  - o Dispense 2 cycles of Palbociclib
  - o Prescribe Tamoxifen (commercial supply)

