### 12.5. Analysis of Secondary Endpoints

Characterize safety and tolerability of palbociclib and tamoxifen in first line therapy for subjects with HR(+)/HER2(-) advanced breast cancer who have not received prior systemic anti-cancer therapies for their advanced/metastatic disease.

 Proportion of subjects with each grade of adverse events as defined by CTCAE v4 will be computed along with 95% confidence intervals, and reported in a tabular and descriptive manner.

Assess response rate based on RECIST 1.1 or MDA Criteria. The response rate (complete or partial response) and 95% confidence interval for the response rate will be computed using PROC FREQ in SAS (Cary, NC).

Evaluate clinical benefit rate RR (complete, partial response, or stable disease) based on RECIST 1.1 or MDA Criteria in subjects with HR(+)/HER2(-) advanced breast cancer who have not received prior systemic anti-cancer therapies for their advanced/metastatic disease treated with palbociclib in combination with tamoxifen.

• Clinical benefit rate (complete, partial response, or stable disease) will be assessed every 8 weeks +/- 1 week while on study treatment using RECIST 1.1 (section 8) or MDA Criteria (for patients with bone only disease). Response will be recorded as disease control rate (DCR), or stable disease plus partial response plus complete response, and reported via waterfall plot. The response rate and 95% confidence interval for the response rate will be computed using PROC FREQ in SAS (Cary, NC).

Measure 2-year overall survival (OS) in subjects with HR(+)/HER2(-) advanced breast cancer who have not received prior systemic anti-cancer therapies for their advanced/metastatic disease treated with palbociclib in combination with tamoxifen.

Median OS times will be computed, and OS rate will be calculated with associated 95% confidence intervals. Kaplan-Meier curves will be plotted. Data will be analyzed using the PROC FREQ and PROC LIFETEST in SAS.

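### Disease assessments follow Day 1 of numbered cycles, so a toxicity or surgery delay that moves a cycle also moves the scan; section 12.5 separately states an 8-week interval that the calendar abandons from cycle 22.

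*Combined protocol and SAP*

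**What the plan says.** Imaging is scheduled by cycle number only. For the first phase, footnote 8 of the section 7 calendar reads "Disease assessment will be performed on Day 1 of every 2 cycles starting at cycle 3", and for the later phase "Disease assessment will be performed on Day 1 of every three cycles starting at cycle 22". Sections 7.3 and 7.4 repeat this with a window of 7 days either side. A cycle is 28 days.

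Two rules can move a cycle start:

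- Section 6.1.1, Table 2, for Grade 3 hematologic toxicity: "Withhold initiation of next cycle". Counts are repeated a week later, and the subject is discontinued if the toxicity has not resolved within 4 weeks of the last study drug administration.
- Section 5.5, for elective surgery: "The next cycle of treatment may be delayed up to 4 weeks to allow for additional recovery".

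Section 8.4.6 dates PFS at the first documented progression, or at death. Section 12.5 says that clinical benefit "will be assessed every 8 weeks +/- 1 week while on study treatment using RECIST 1.1". No passage says whether scans hold their calendar date when a cycle is delayed.

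**The concern.** Progression is dated at the scan that shows it, so whatever moves the scan moves the recorded PFS. Here one driver of scan timing is toxicity. The protocol expects delays to be common. For the earlier randomized phase II trial of palbociclib plus letrozole, section 1.1 reports: "Dose delay was required in 45 % of patients in the combination arm and dose reduction was required in 40% of patients". Section 10.1 reports a Grade 3 or higher neutrophil decrease in 66% of patients.

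In a randomized comparison, much of such a lag could be shared by the control arm. This trial has no control arm. It is sized against a historical median of 15 months, progression is assessed locally, and section 12.4 plans no sensitivity analysis for the timing of assessments.

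The 24-week clinical benefit rate uses the same scans. Cycle 7 Day 1 falls exactly at week 24 when nothing is delayed, so a delay moves that assessment as well.

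**Working it through.** **1. The plan's own figure.** Inputs from section 12.3: medians 15 and 25 months, one-sided 0.05, 80% power, exponential model, 24 months' accrual plus 24 months' follow-up, 20% loss.

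- Hazards: λ0 = ln 2/15 = 0.04621 and λ1 = ln 2/25 = 0.02773 per month.
- Event probabilities under uniform accrual: p = 1 − (e^(−24λ) − e^(−48λ))/(24λ), giving p0 = 0.801 and p1 = 0.625.
- n = [1.645·λ0/√p0 + 0.842·λ1/√p1]² / (λ0 − λ1)² = 38.35, and 38.35/0.8 = 47.9.

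This rounds up to the stated 48.

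**2. Nominal scan dates.** Day 1 of cycle c falls at week 4(c − 1).

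| Cycle | 3 | 7 | 19 | 22 | 25 |
|---|---|---|---|---|---|
| Week | 8 | 24 | 72 | 84 | 96 |

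Intervals are 8 weeks up to week 72. The gap from cycle 19 to cycle 22 is 84 − 72 = 12 weeks, and later gaps are also 12 weeks. Section 12.5's 8 weeks plus or minus 1 week therefore fails after week 72 with no delay at all. Before week 72, two one-week delays in an interval make it 10 weeks, which is also outside that tolerance.

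**3. One delayed interval.** If progression is about equally likely throughout an interval of L weeks, the mean lag to detection is L/2. One delay of d weeks makes it (8 + d)/2, so the extra mean lag is d/2.

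| Delay d (weeks) | 0 | 1 | 2 | 4 |
|---|---|---|---|---|
| Mean lag (weeks) | 4.0 | 4.5 | 5.0 | 6.0 |
| Extra lag (weeks) | 0 | 0.5 | 1.0 | 2.0 |
| Extra lag (months) | 0 | 0.11 | 0.23 | 0.46 |

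The shift is d/2 rather than d because a later scan also picks up progressions that occur during the delay, which the undelayed schedule would have found only at its next visit.

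**4. Whole schedule, 45% of subjects delayed.** The documents give neither the number nor the length of delays per subject, so these are assumed: 1-2 weeks in 25-100% of the affected subjects' cycles. True PFS is exponential with median 15 or 25 months. Compared with scans on fixed dates, mean recorded PFS for events in the first 24 months rises by about 0.01-0.18 month. In the 25% case at a true median of 15 months, about 15% of these subjects are recorded earlier than on fixed dates and 23% later. The recorded median goes from 16.6 to 16.3 months, that is, down.

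The median falls because of the grid. A true median of 15 months is week 65, between the scans at weeks 64 and 72, so without delays the recorded median sits on week 72 (16.6 months). Delays spread the scan dates and remove that step.

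**5. Whole schedule, every subject at risk of delay.** Assumed: 10-100% of cycles delayed by 1 week, 25% by 2 weeks, or 10-25% by 4 weeks. Mean lag to detection rises from 4.9 weeks to 5.0-6.3 weeks at a true median of 15 months, and from 5.1 to 5.2-6.6 weeks at 25 months. The increase is at most about 1.5 weeks (0.3 month).

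The one-sided type I error of the exponential test was simulated with 48 subjects, no drop-out and analysis at 48 months (20,000 trials, Monte Carlo standard error about 0.002):

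| Progression dates | Type I error |
|---|---|
| Exact | 0.043 |
| 8-week scans throughout | 0.061 |
| Protocol schedule, no delays | 0.068 |
| Protocol schedule with delays | 0.070-0.077 |

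**The case against.** The strongest reply is that the effect is immaterial. A mean shift of under 0.2 month is negligible beside 15 versus 25 months, and most of the type I error inflation (0.043 to 0.068) comes from scanning at intervals at all, which re-anchoring would not remove. That stands, and it makes this a minor point.

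The sentence in section 12.5 also concerns clinical benefit, which turns on 24 weeks, so the switch at cycle 22 does not touch that endpoint. That stands too, although the text still contradicts the calendar and the same scans feed PFS.

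Four stronger readings are tempting, and the documents do not support them:

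- A reader might infer that every dose delay postpones a scan. Only the Grade 3 hematologic row of Table 2 explicitly withholds the next cycle. Other rows call for a hold without saying that cycle numbering moves, and a mid-cycle hold need not move Day 1. Section 10.1 gives a median duration of 7 days for Grade 3 or higher neutropenia. The window of 7 days can offset a delay of that length, though it does not require this and equally allows a later scan.
- A reader might infer that the error always favours the combination. It does so on average only. With scans at weeks 10 and 18 instead of 8 and 16, a progression at week 9 is recorded at week 10 rather than week 16.
- A reader might take the two 4-week limits to mean that every cycle could slip 4 weeks. If the Table 2 limit runs from the Day 21 palbociclib dose, it ends at Day 49, which is 20 days after the due Day 29. Elective surgery would not plausibly recur each cycle.
- A reader might think that 19 cycles cannot be 18 months, because cycle 19 Day 1 is at 16.6 months. As a duration, 19 × 28 = 532 days is 17.5 months, a fair rounding.

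**Conclusion.** The point holds as a minor one. Scan timing is tied to cycle starts that toxicity or surgery can move, and nothing in the plan prevents this. Under the assumed delay patterns, recorded PFS lengthens on average by about 0.01-0.18 month when 45% of subjects are affected, and by at most about 0.3 month when all are at risk. The recorded median can go either way. Neither the sample size nor a 15 versus 25 month comparison is overturned.

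These sizes rest on assumed delay frequencies and lengths, and on exponential PFS. The 45% figure comes from a different combination and says nothing about delays per cycle.

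The contradiction between section 12.5 and the 12-week interval from cycle 22 needs no assumption. The hold rules themselves are not in question.

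**What to change.** In footnote 8, sections 7.3 and 7.4 and the calendar, schedule disease assessments in weeks from Cycle 1 Day 1: every 8 weeks (±7 days) through week 72, then every 12 weeks (±7 days) from week 84, regardless of palbociclib holds or cycle delays. These are the dates the present schedule gives when no cycle slips. State the same schedule in section 12.5.

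Section 9 describes blood collection, including at progression, in the past tense, so many scans may already have been done and cannot be re-dated. For those, report the actual scan intervals and add a sensitivity analysis of PFS that treats progression as interval-censored between the last progression-free scan and the scan that showed it.

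The cost is a wording amendment and one additional analysis. The number of scans is essentially unchanged. The one practical drawback is that some scans will no longer coincide with a delayed Day 1 visit.

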# 7.1. Screening

# 7.1.1. Within 28 days prior to registration for protocol therapy

- Informed consent, HIPAA authorization
- Medical history including prior therapies and pathology
- Physical exam, height, weight
- Vital signs (blood pressure, heart rate, temperature)
- ECOG performance status
- Concomitant medications
- CT/MRI chest, abdomen, pelvis
- CT or MRI of brain, if clinically indicated
- Whole body bone scan
- If bone lesion detected from whole body bone scan, bone X-ray, CT, or MRI of the largest bone lesion
- If skin lesion detected by physical exam, skin color photography

# 7.1.2. Within 14 days prior to registration for protocol therapy

- Blood chemistries (sodium, potassium, serum creatinine, calcium, albumin, ALT, AST, bilirubin, alkaline phosphatase.)
- Platelets, ANC and hemoglobin

# 7.1.3. Within 72 hours prior to registration for protocol therapy

• Pregnancy test for women of childbearing potential (WOCP). A negative serum or urine pregnancy test is required within 72 hours of study registration. If the urine test is positive or cannot be confirmed as negative, a serum pregnancy test will be required.

#### 7.2. On Treatment

#### 7.2.1. Day 1 of Cycle 1

**Note:** Cycle 1 Day 1 lab testing need not be repeated if completed within 7 days of starting protocol therapy.

- Physical exam, weight
- Vital signs
- ECOG performance status
- Blood chemistries (sodium, potassium, serum creatinine, calcium, albumin, ALT, AST, bilirubin, alkaline phosphatase)
- Platelets, ANC and hemoglobin
- Pregnancy test for women of childbearing potential (WOCP), if clinically indicated. If
  the urine test is positive or cannot be confirmed as negative, a serum pregnancy test
  will be required.
- Assess adverse events (AE)
- Concomitant medications
- Dispense Palbociclib
- Prescribe Tamoxifen (commercial supply)

• Correlative and Banking samples. See CLM for collection, labeling, processing, and shipping instructions.

# 7.2.2. Day 15 of Cycle 1 (±3 days)

• Platelets, ANC and hemoglobin

# 7.2.3. Day 1 of Cycle 2 ( $\pm 3$ days)

- Physical exam, weight
- Vital signs
- ECOG performance status
- Blood chemistries (sodium, potassium, serum creatinine calcium, albumin, ALT, AST, bilirubin, alkaline phosphatase)
- Platelets, ANC and hemoglobin
- Pregnancy test for women of childbearing potential (WOCP), if clinically indicated. If
  the urine test is positive or cannot be confirmed as negative, a serum pregnancy test
  will be required.
- Assess adverse events
- Concomitant medications
- Dispense Palbociclib
- Prescribe Tamoxifen (commercial supply)

# 7.2.4. Day 15 of Cycle 2 ( $\pm 3$ days)

• Platelets, ANC and hemoglobin

# 7.2.5. Day 1 of Cycle 3-5 (±3 days)

- Physical exam, weight
- Vital signs
- ECOG performance status
- Blood chemistries (sodium, potassium, serum creatinine calcium, albumin, ALT, AST, bilirubin, alkaline phosphatase)
- Platelets, ANC and hemoglobin
- Pregnancy test for women of childbearing potential (WOCP), if clinically indicated. If
  the urine test is positive or cannot be confirmed as negative, a serum pregnancy test
  will be required.
- Assess adverse events
- Concomitant medications
- Dispense Palbociclib (dispense 2 cycles at cycle 5)
- Prescribe Tamoxifen (commercial supply)
- Correlative blood sample: cycle 5 day 1

